3.3.4 Study Visits

3.3.4.1 Screening

Only patients who had already independently agreed to undergo BKPro surgery were approached by the trial team about participation in the study.

At V01, the Investigator conducted the informed consent process (Section 12.1), ensuring that the subject's signature had been obtained on the patient informed consent (PIC) form and that the subject had received a copy before any study specific procedures are conducted. Once the PIC was signed, the subject was assigned a patient number (Section 8.2) and the Investigator determined if the subject met the eligibility criteria, surgery (V02) was scheduled and the screening fax form completed and faxed to the sponsor.

In addition, the following procedures were performed at the screening visit:

- Collection of background information about the subject including: demographics, medical history with prior treatments and current medications.
- Pregnancy test, when applicable
- External eye photography
- Anterior Segment assessments (slit-lamp biomicroscopy)
- Optical biometry, including ARGOS-IO implant size assessment
- Posterior Segment assessments (biomicroscopy, PS-OCT if feasible)
- IOP measurement with GAT and pneumotonometry
- Instruction of subjects on the need to report as soon as possible any SAEs occurring at any time during the study (starting from Visit 02 surgery)
- Completion the screening fax form and send to sponsor
- Completion of the eCRF.

3.3.4.2 Surgery

The following procedures might be carried out one day before surgery (in subjects already hospitalized for the surgery) or on the day of surgery:

- Verification that the subject continues to meet eligibility criteria

 Implantata Ophthalmic Products GmbH	Clinical Investigation Report ARGOS-KP01	Revision A Page 39 of 114
--	---	----------------------------------

- For female subjects of childbearing potential: collection of urine for pregnancy test. A test done within 24 hours prior to surgery had to be negative
- Performance of external eye photography prior to surgery.

The following procedures were performed on the day of the surgery:

- BKPro and ARGOS-IO pressure sensor implantations, including the updating medical history (up to surgery) and recording of concomitant medications, device deficiencies or malfunctions (including those detected during device preparation) and any AEs (starting from implantation of the ARGOS-IO pressure sensor)
- Completion of the implantation procedure questionnaire (surgeon) and the eCRF
- Completion of the patient inclusion form and fax it to the sponsor
- Instruction of subjects on the need to promptly report any SAE that may occur at any time during the study.
- Schedule Visit 2 (V02).

The duration of the subject's hospitalization was at the discretion of the Investigator. Durations of up to 7 days were not considered in themselves to be SAEs.

3.3.4.3 Follow-up, including duration

Following surgery, patients attended a total of 13 follow-up visits (Day 1 until Week 52). The main purpose of the follow-up visits was to assess eye condition and to determine if the patients had experienced any AEs. In addition, IOP was measured with the ARGOS-IO system beginning on Day 1 (V2) at the clinic to permit assessment of the performance of the ARGOS-IO pressure sensor and from week 4 (V7) ARGOS-IO home measurements were performed as well. V7, V9, V11 and V15 surgical manometry and ARGOS-IO measurements were performed at the same time point.

A detailed listing of the visit schedule and main activities conducted at each can be found in the assessment schedule in Table 1.

3.4 Treatment Allocation

This was a single-arm open-label study. No randomization and blinding/masking procedures were used in this study. To avoid bias resulting from patient selection, all consecutive patients potentially meeting the eligibility requirements were informed of the study and asked to participate. Those agreeing underwent the informed consent procedure and if they consented, was screened. All eligible patients were enrolled.

 Implantata Ophthalmic Products GmbH	Clinical Investigation Report ARGOS-KP01	Revision A Page 40 of 114
--	---	----------------------------------

Measurements of IOP with the ARGOS-IO sensor was compared to IOP measured with surgical manometry in the same subject at the same time point to allow assessment of performance.

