3.3.3.11 Intraocular pressure (IOP) measurement

Intraocular pressure (IOP) was measured using four techniques. To provide a baseline IOP measurement, both Goldmann Applanation Tonometry (GAT) and pneumotonometry were performed at V01 (screening) if possible. Beginning at V03 (first follow-up visit), IOP measurement was performed with the ARGOS-IO system, both by site personnel at clinic visits and after discharge

 Implantata Ophthalmic Products GmbH	Clinical Investigation Report ARGOS-KP01	Revision A Page 37 of 114
--	---	----------------------------------

from hospital by the subject at home between visits. Direct manometry was performed at visits 07, 09, 11 and 15 to allow assessment of the accuracy of the ARGOS-IO system.

After surgery, treatment decisions was based on direct manometry, supplemented by finger palpation.

IOP measurement in the clinic

On the occasions when IOP was measured with both ARGOS-IO and manometry, it was measured as a series consisting of first with ARGOS-IO prior to positioning of the operating microscope, then manometry and followed again by ARGOS-IO. At the other follow-up visits IOP was measured with ARGOS-IO at least two times at every visit preferably at the beginning and end of the visit.

The surgical manometry measurements was conducted in the surgical suite under an operating microscope. A manometry system utilizing sterile saline solution was implemented via a 21-gauge needle cannulated to the anterior chamber. A standard procedure was followed both during the preparation of the system and the measurement in order to minimize the possibility of leaks or trapped air in the system.

At follow-up visits where manometry was not performed, the physician also estimated IOP using finger palpation, categorizing pressure as soft/hypotonic, definitely normal, borderline or definitely hypertonic.

ARGOS-IO system measurement by the subject at home

While in the clinic following surgery, subjects received detailed instruction in the use of the Mesograph reading device. Upon discharge from the clinic, they received an individual Mesograph reading device, a copy of the instructions for use and the Multiline Connector to perform self-tonometry at home. Subjects were requested to perform at least 4 IOP measurements with the Mesograph daily, evenly spread throughout the day.

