3.2.2. Blinding

This is an open label, non-comparative study with one treatment group. No blinding is requested.

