9.1. Primary Performance Endpoint

Primary performance endpoint is the level of agreement between IOP measurements made using manometry and the ARGOS-IO system over the first 12 months following implantation of the IMD.

A Bland-Altman analysis will be done for a point estimation of the level of agreement between the two IOP measurement methods with repeated observations. It is assumed that the true IOP value varies over time for each patient.

Concerning ARGOS-IO, the average of the (three) measurements during surgical manometry will be taken.

All complete measurement pairs (manometry value, average of the ARGOS-IO values during surgical manometry) will be used per patient, to calculate the mean within subject difference between the methods. Pairs of measurement will only be used when there was no more than 2 minutes difference between both measurements.

The average over the mean within subject differences (Δ) is an estimate for the bias between the two IOP measurement methods. The lower and the upper level of agreement will be estimated as

$$\text{LoA}_{\text{low}} = \Delta - z_{\beta/2} * s$$

$$\text{LoA}_{\text{upp}} = \Delta + z_{\beta/2} * s$$

($z_{\beta/2}$ is the upper $\beta/2$ quantile of the standard normal distribution ($=1.96$), s is an estimate for the variation of the differences which comprises both between and within individual components, see Zou, section 2.1.1)

95% confidence interval estimation for the lower limit of agreement (LoA_{low}) and for the upper limit of agreement (LoA_{upp}) will be obtained using the MOVER method, see Zou, section 2.2.2.

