9.6. Unplanned Analysis

Summary statistics will be presented in a table by visit (Week 4, 16, 28, 52 visit) and time point (measurement 1 - prior to manometry, measurement 2 - during manometry, measurement 3 - following manometry) for the within subject mean IOP values. Concerning each patient and time point, the maximal difference between the IOP values will be derived and summarized in the table.

Concerning each post-surgery visit, the within subject mean IOP value will be derived for measurement 1 (at the beginning of the visit). Summary statistics will be tabulated for the within subject mean IOP value by the result of finger palpation assessment of IOP (soft/ hypotonic, borderline, normal, hypertonic). Furthermore, within subject mean IOP value and finger palpation assessment will be presented per patient in a scatter plot.

10. Safety Analyses

All safety parameters will be evaluated on the SFS. Only descriptive statistics will apply.

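### No masking of the manometry reader or the palpating physician is described, so a known ARGOS-IO value could influence either comparator, palpation more than manometry

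*Protocol*

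**What the plan says.** **Masking.** Protocol 3.4 says: "No randomization and blinding/masking procedures were used in this study". SAP 3.2.2 says: "No blinding is requested". The SAP's reason is that there is only one treatment group. Neither document discusses keeping the result of one pressure method from the person recording another.

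**Manometry visits (V7, V9, V11, V15).** Protocol 3.3.3.11 gives the series as "first with ARGOS-IO prior to positioning of the operating microscope, then manometry and followed again by ARGOS-IO". For the primary performance endpoint, SAP 9.1 specifies: "Concerning ARGOS-IO, the average of the (three) measurements during surgical manometry will be taken". It adds: "Pairs of measurement will only be used when there was no more than 2 minutes difference between both measurements".

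**Other follow-up visits.** Protocol 3.3.3.11 asks for at least two ARGOS-IO readings, preferably one at the start and one at the end of the visit. It also says that "the physician also estimated IOP using finger palpation", in four categories from soft/hypotonic to definitely hypertonic. It does not say which comes first. For the palpation comparison SAP 9.6 says that, for each post-surgery visit, "the within subject mean IOP value will be derived for measurement 1 (at the beginning of the visit".

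**Use of the result.** Protocol 5.5 cites the palpation comparison under accuracy, precision and sensor drift, and reports a significant difference in telemetric IOP between palpation categories. Section 5.3 also reports good consistency with palpation. The limitations in 5.1 name fluid loss and operator experience for manometry. They mention neither masking nor palpation.

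**The concern.** When agreement between two methods is the endpoint, each result should be obtained without knowledge of the other. A single-arm design explains why treatment is not blinded. It does not explain why the comparator reading is left unprotected.

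Palpation is the more exposed comparator. Protocol 1.2 describes its values as highly subjective, and a physician who knows the telemetric value can place a borderline eye in the matching category. Part of the association reported in 5.5 could then come from the device itself. Manometry is the comparator for the primary performance endpoint, so even a small influence there would affect the limits of agreement on which the performance conclusion rests.

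**Working it through.** The plan states no figure on this point, so there is none to reproduce. The check has two parts: what the documents establish, and which way an influence would act.

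**1. What is established**

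| Question | Manometry | Palpation |
|---|---|---|
| Is the comparator's reader masked? | No (Protocol 3.4, SAP 3.2.2) | No (same) |
| Is a device reading taken before or alongside the comparator? | Yes: before (Protocol 3.3.3.11) and during (SAP 9.1) | Order not stated; the device value used is from the start of the visit (SAP 9.6) |
| Can a device value be seen? | The reader has a display (questionnaire in 4.7.2) | Same; physicians can also read home values at any time (2.2.2), and staff download them at each visit (3.3.3.11) |
| Is it stated that the value was seen, or hidden? | Neither | Neither |
| How open is the comparator to influence? | Instrument reading with a standard procedure | Subjective grade in four categories |
| Role | Primary performance endpoint | Headed unplanned in SAP 9.6, but cited in 5.5 |

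**2. Direction, manometry (illustration; all SDs, offsets and weights are assumed)**

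Let M be the manometry value that would be recorded without knowledge of the device, A the ARGOS-IO value, and w the fraction by which the reader moves towards A.

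*Pull towards the values seen during manometry.* The recorded value is M' = M − w(M − A), so M' − A = (1 − w)(M − A). The bias and the half-width of the limits, 1.96 × SD, both shrink by (1 − w). Half-widths in mmHg:

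| SD of differences | w = 0 | w = 0.10 | w = 0.25 | w = 0.50 |
|---|---|---|---|---|
| 2 | 3.92 | 3.53 | 2.94 | 1.96 |
| 4 | 7.84 | 7.06 | 5.88 | 3.92 |
| 6 | 11.76 | 10.58 | 8.82 | 5.88 |

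For example, 0.75 × 1.96 × 4 = 5.88.

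*Pull towards the pre-manometry reading only.* That reading is not in the analysed average. Assume an ARGOS-IO offset of 2 mmHg, between-eye device SD 2.5, single-reading SD 1, manometry SD 3, and three readings averaged. Then:

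- Mean difference = −(1 − w) × 2
- Variance = (1 − w)² × (3² + 2.5²) + w² × 1² + 1²/3

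With w = 0 the variance is 15.25 + 0.333 = 15.583 and the half-width is 1.96 × 3.948 = 7.74. With w = 0.25 it is 8.578 + 0.0625 + 0.333 = 8.974, giving 1.96 × 2.996 = 5.87, and the mean difference moves from −2.0 to −1.5. Agreement is again flattered.

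*Where the direction can reverse.* Protocol 3.3.1 and 5.1 say that puncture can lose aqueous humor and change the pressure. If pressure falls by d between the pre-manometry reading and the analysed readings, and the device offset is b, the mean difference (manometry minus ARGOS-IO) is −(1 − w)b + wd. With b = 0, d = 5 and w = 0.25 it goes from 0 to 1.25 mmHg, which is a worse bias. So a flattering direction is assured only for a pull towards the values seen during the procedure.

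**3. Palpation**

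I give no figure. The grade has four categories, and SAP 9.6 tabulates IOP by category. Any number would need an assumed grading error and an assumed weight on the device value, and the documents support neither. In direction, moving a grade towards the category that matches a known telemetric value sharpens the separation between categories.

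**The case against.** A reader might infer that operators saw the ARGOS-IO value and that palpation was graded after it. The documents say neither. The display and the lack of masking make it possible. The start-of-visit reading makes the order plausible, but Protocol 3.3.3.11 only prefers a reading at the start. The full investigation plan (Annex A) is not among the documents and may settle the order. This objection stands: the point concerns a missing safeguard, not an observed bias.

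It can also be said that the pre-manometry reading is not in the analysed average, that manometry is an instrument reading, and that the remark in 5.1 on the investigator's experience concerns skill rather than expectation. All three hold, and they are why the manometry risk is rated the smaller one. They do not remove it, because the averaged readings are taken during manometry and nothing keeps them from the person recording it.

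A further inference would be that changing the order of measurement would cure the problem. It would not. The analysed ARGOS-IO values are concurrent with manometry, so no reordering separates them; what helps is when the values are viewed. For palpation, grading first leaves knowledge of home and earlier readings.

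Finally, palpation is in no primary or secondary endpoint. That limits the consequence for the plan, but 5.5 gives it weight as accuracy evidence and 5.1 does not qualify it. The objection therefore fails for the report's conclusions.

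**Conclusion.** The concern holds as an unaddressed and undisclosed risk of bias. No masking of either comparator's reader is described. Device readings come before and during manometry, and the order of palpation relative to the device is not fixed. The risk is mainly for palpation and smaller for manometry.

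The size cannot be estimated from the documents. The mmHg values above show only how an assumed pull would carry through to the limits of agreement. Agreement would be flattered if the pull is towards values seen at the same time; the direction is not fixed if only the pre-manometry reading is known. It should be corrected, but it does not show that the agreement results are wrong.

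**What to change.** **For the procedure (Protocol 3.3.3.11, and any later investigation).**

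- Record the palpation grade before the Mesograph is activated and before home readings are downloaded at that visit.
- Write down the manometry value before its reader views the ARGOS-IO values of that series. The Mesograph stores about 3,000 readings, so the values can be retrieved afterwards.
- Leave the simultaneous readings and the 2-minute window as they are.

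Protocol 3.3.3.11 bases treatment decisions after surgery on manometry, supplemented by palpation, so the documents state no need to see the device value first.

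**For the completed study.** Add to 5.1 that neither the manometry reader nor the palpating physician was masked to ARGOS-IO values. In 5.5, do not present the palpation comparison as independent evidence of accuracy.

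**Cost.** A few sentences on the order of recording and viewing, with no added measurement or visit and no additional staff in principle. The documents do not say whether the display can be suppressed, so it may have to be kept out of the manometry reader's view. The change reduces the risk but does not remove it, since earlier and home readings may already be known.

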3.5 Data Quality Assurance

The study was monitored in compliance with the Declaration of Helsinki, ISO 14155:2011, the Clinical Investigation Plan (CIP) and all applicable national and local regulations. All monitoring activities were conducted by trained and qualified monitors, who documented each individual monitoring visit. In general, during monitoring visits the monitor ensured that the study is being conducted according to the CIP, ISO 14155:2011, ICH GCP (International Conference on Harmonisation Good Clinical Practice) and other applicable regulations, and compared the CRF entries to original source data. He/she also made sure the informed consent procedure had been appropriately carried out and ensured that all SAEs had been reported within applicable timeframes. He/she also ensured that investigational device accountability had been maintained and, after completion of the study, performed final accountability and arranged return or destruction of investigational products. Detailed monitoring procedures are described in a separate monitoring plan.

Data were collected through an electronic Case Report Form (eCRF) provided by the sponsor or its designee to the centers prior to study start. The site entered study data directly into the eCRF during or as soon after the visit as possible.

The investigator was responsible for maintaining accurate, complete, and up-to-date records for each subject. This includes maintaining any source documentation related to the study. The anonymity of participating subjects had to be maintained. The sites maintained a list of the subjects' names and the Patient ID assigned to each individual patient. Documents that identified the subject beyond the Patient ID were not submitted to the sponsor (e.g. the signed informed consent document) and had to be maintained in strict confidence by the investigator, except to the extent necessary to allow inspections by the regulatory authorities and audits by the study monitor or sponsor representatives.

The investigator had promptly reviewed the completed eCRFs for each subject promptly and had to confirm the accuracy of all data entered with his/her signature at the end of each documented subject's visit in the eCRF. Any corrections made to data entries were GCP conform.

During data review, data management generated queries for any missing, out of range or questionable data and sent these to the investigator for resolution. The physician answered the query and this answer was documented. All queries had to be answered and the database locked before any (interim) analysis of the data.

 Implantata Ophthalmic Products GmbH	Clinical Investigation Report ARGOS-KP01	Revision A Page 41 of 114
--	---	----------------------------------

It had been verified by the sponsor that only validated and secure electronic data systems were used in this clinical investigation. Electronic data systems included the clinical data management database and the ARGOS-IO system measurement database. Database validation and security followed the respective national and international requirements.

3.6 Statistics

Statistical design, method and analytical procedures

The primary purpose of this investigation is to assess safety of the investigational device.

Demographic and baseline characteristics

Demographic characteristics (age, sex, educational level), pre-existing glaucoma, secondary glaucoma to BKPro, pressure lowering surgeries incl. GDD prior to BKPro, GDD post BKPro, anti-glaucoma medication, and other previous and concurrent treatments are tabulated for the safety set.

Patient Disposition

The number and percentage of screened, enrolled and implanted subjects, as well as those who completed the follow-up are tabulated for the safety set. The number and percentage of screen failures and early withdrawals is also tabulated, along with the reason for the screen failure or drop-out.

Safety Analysis

The incidence within the safety population was estimated with a 95% confidence interval (Pearson-Clopper, two-sided).

Performance Analysis

The Bland-Altman method, which compares the mean of paired measurements to their difference, was used to determine the upper and lower limits of agreement expected to contain 95% of the IOP value pairs obtained with ARGOS-IO and surgical manometry. The two-sided 95% confidence intervals for each of these limits were calculated using the Mover method (Zou, Confidence interval estimation for the Bland-Altman limits of agreement with multiple observations per individual, 2011) to account for repeated observations of a changing value in individuals. IOP values were plotted both as Bland-Altman plots of individual measurement pairs, and by measurement technique as time plots of both population means and individual participant values.

IOP Implandata Ophthalmic Products GmbH	Clinical Investigation Report ARGOS-KP01	Revision A
		Page 42 of 114

The level of agreement was calculated to provide an estimate of the agreement, and eventually a correction factor to allow direct comparison of values obtained with different methods.

 Implantata Ophthalmic Products GmbH	Clinical Investigation Report ARGOS-KP01	Revision A Page 43 of 114
--	---	----------------------------------

